## 9.4 Statistical Methods

### 9.4.1 Analysis of Efficacy

#### 9.4.1.1 Primary efficacy analyses

For each shoulder condition, the primary AUC endpoint will be calculated and comparisons will be estimated from an Analysis of Covariance model with parameters for treatment group, Baseline average daily shoulder pain with movement score, and analysis site. In addition, the model for shoulder AC will also include a covariate for pain duration since onset. Full details of the AUC analyses will be detailed in the SAP.

#### 9.4.1.2 Secondary efficacy analyses

The key secondary change from Baseline endpoints will be analyzed with longitudinal mixed models for repeated measures with fixed effects for treatment group, study week, treatment-by-week interaction, analysis site, and Baseline score. Patient will be the random effect. Treatment differences from control will be estimated via LSMs from the analysis model along with 95% CIs and associated 2-sided p-values. This model assumes data are missing at random and includes only observed data. In addition, the model for shoulder AC will also include a covariate for pain duration since onset.

Multiplicity will be addressed by analyzing the key secondary endpoints sequentially in the order presented in the protocol, testing each endpoint at the nominal  $\alpha = 0.05$ , 2-sided level to ensure overall type I error control at the 2-sided 0.05 level.

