### 5.3 Randomization and Blinding

Patients from each shoulder condition will be randomized on Day 1 to 1 of 2 treatment arms (FX006 or placebo) using centralized randomization accessed through an interactive voice/web response system randomization (IxRS) module.

Glenohumeral OA patients will be stratified by the Baseline average daily shoulder pain with movement score (0 to 10 NRS) (5.0 to <7.0 or ≥7.0 to 9.0). Shoulder AC patients will be stratified by the Baseline average daily shoulder pain with movement score (0 to 10 NRS) (5.0 to <7.0 or ≥7.0 to 9.0) and pain duration since onset at Screening (1 to 3 months, inclusive, or >3 to ≤6 months).

The blinded-assessor technique will be used in this study to maintain double-blind conditions. Key study site staff roles are defined below and a site-specific blinding plan will be developed to ensure the blind is maintained throughout the duration of the study. Treatments will be prepared by an unblinded pharmacist/coordinator who has experience with the preparation of study medication and who has been properly trained by the Sponsor or designee. Intra-articular injections will be performed by an unblinded injector.

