#### 7.1.2 Secondary Efficacy Endpoints

The secondary efficacy endpoints comparing FX006 to placebo for each of the shoulder conditions (glenohumeral OA and shoulder AC) in this study include the following:

- Change from Baseline in the weekly mean of the average daily shoulder pain with movement score at Week 12
- Change from Baseline in the SPADI pain subscale at Week 12
- Change from Baseline in the SPADI disability subscale at Week 12
- The PGIC score at Week 12
- Change from Baseline in the ROM of external rotation at Week 12

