#### **9.1.1 Demographics and Baseline Characteristics**

Demographic and Baseline characteristics will be listed by study site and patient and will be summarized by treatment.

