#### 9.4.3 Interim Analyses

For each shoulder condition, a blinded interim analysis will occur when approximately 50% of the patients have completed Week 8 to determine the need for a potential adjustment to the sample sizes. Prior data suggest the standard deviation of the primary endpoint could range from 2 to 2.5. Therefore, the interim analyses will enable a sample size increase up to 150 in each shoulder condition to ensure the desired statistical power is obtained.

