#### 9.4.5 Subgroups and Covariates

Preplanned subgroup analyses including aspiration status, OA grade based on the Samilson-Prieto classification system, gender, and Baseline average daily shoulder pain with movement score will be detailed in the SAP. In addition, subgroups of pain duration since onset are preplanned for shoulder AC patients. Further subgroups may be defined and explored after all preplanned analyses have been completed to further elucidate study results.

Covariates for efficacy analyses will include Baseline average daily shoulder pain with movement score, Baseline score for the endpoint, analysis site, and, for AC patients, pain duration since onset. Other covariates may be explored and will be fully defined in the SAP.

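### Section 9.4.1.2 gives the SPADI and external rotation models one baseline term where 9.4.5 lists two; the missing one, baseline pain, is a randomisation factor

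*Combined protocol and SAP*

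**What the plan says.** Section 9.4.1.2 fits mixed models for repeated measures with "fixed effects for treatment group, study week, treatment-by-week interaction, analysis site, and Baseline score", patient as the random effect, and pain duration added for adhesive capsulitis (AC). Section 9.4.5, in words that the synopsis repeats, says: "Covariates for efficacy analyses will include Baseline average daily shoulder pain with movement score, Baseline score for the endpoint, analysis site", again with pain duration for AC.

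Baseline pain is also a design variable. Section 5.3 says: "Glenohumeral OA patients will be stratified by the Baseline average daily shoulder pain with movement score (0 to 10 NRS". The AC cohort is stratified by the same score and by pain duration.

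Section 7.1.2 lists five secondary endpoints. Four are changes from Baseline at Week 12: pain with movement, SPADI pain, SPADI disability, and the last, "Change from Baseline in the ROM of external rotation at Week 12". The fourth in order, PGIC, is not a change from Baseline and is outside this point. Multiplicity is handled by "analyzing the key secondary endpoints sequentially in the order presented in the protocol", each at two-sided 0.05.

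**The concern.** Someone programming from 9.4.1.2 would adjust the SPADI and range-of-motion models for the endpoint's own baseline only. Someone programming from 9.4.5 would also adjust for baseline pain. Neither section says which governs.

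Two things are at stake. First, these endpoints stand second, third and fifth in a fixed sequence, where one p-value above 0.05 stops every later test. The choice of covariates can therefore change how far the sequence runs. Second, when randomisation is stratified on a variable that predicts the outcome, leaving that variable out of the model gives away precision that the design has already secured. In AC, 9.4.1.2 carries one stratification factor (pain duration) but, for these endpoints, not the other.

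**Working it through.** **1. The two covariate lists, endpoint by endpoint**

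| Endpoint (7.1.2) | Baseline term, 9.4.1.2 | Baseline terms, 9.4.5 | Same model? |
|---|---|---|---|
| Week 12 pain | baseline pain | baseline pain (the two coincide) | yes |
| SPADI pain | SPADI pain | SPADI pain + baseline pain | no |
| SPADI disability | SPADI disability | SPADI disability + baseline pain | no |
| External rotation | external rotation | external rotation + baseline pain | no |

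**2. The plan's own power figure.** Section 9.4.6 claims more than 80% power, sized on Week 12 pain. Its inputs are N = 136, difference 1 and SD 2 for osteoarthritis (OA), and N = 114, difference 1.2 and SD 2.1 for AC. With 1:1 allocation the noncentrality is (difference/SD) × √N / 2.
- OA: 0.5 × √136 / 2 = 2.915, power 82.5%.
- AC: 0.571 × √114 / 2 = 3.051, power 85.6%.

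The figure reproduces. The documents give no effect size or power for SPADI or range of motion, so the steps below assume a standardised effect of 0.5 (after adjustment for the endpoint's own baseline) for both cohorts.

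**3. Closed form.** Let r be the partial correlation of baseline pain with the outcome, given the own baseline. Including baseline pain divides the residual SD by 1/√(1 − r²), so the noncentrality rises by the factor 1/√(1 − r²).
- r = 0.1, OA: 2.915 × 1.005 = 2.930, power 82.5% to 82.9%.
- r = 0.1, AC: 0.5 × √114 / 2 = 2.669, × 1.005 = 2.683, power 75.4% to 75.8%.

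The gain is about 0.4 points in each cohort. In patient terms, 1/(1 − r²) is 1.01 at r = 0.1, 1.04 at 0.2 and 1.19 at 0.4.

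**4. Simulation with the stratified design.** There were 6,000 runs per cell, with one complete Week 12 outcome per patient. Assumptions: permuted blocks of 4 within strata, own baseline always in the model, and a correlation of 0.4 between own baseline and baseline pain. Power in %, without / with baseline pain:

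| r | OA, N = 136 | gain | AC, N = 114 | gain |
|---|---|---|---|---|
| 0.2 | 82.4 / 83.6 | 1.2 | 75.0 / 76.3 | 1.3 |
| 0.3 | 83.1 / 85.6 | 2.5 | 76.6 / 79.7 | 3.1 |
| 0.4 | 83.4 / 88.3 | 4.9 | 76.5 / 82.3 | 5.8 |

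The closed form gives slightly larger gains (1.5 and 1.7 points at r = 0.2; 6.0 and 6.9 at r = 0.4). It ignores the partial balance on baseline pain that stratification provides even when the term is left out. At an effect of 0.35 the simulated gains are about 2 to 7 points over the same range of r.

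**5. Type I error and agreement.** With no treatment effect, the model without baseline pain rejects in 3.5% to 4.8% of runs, and the model with it in 4.7% to 5.2%. When an effect exists (0.35 or 0.5) and r is 0.2 to 0.4, the two models fall on opposite sides of 0.05 in 2.6% to 9.6% of trials per endpoint.

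**The case against.** The strongest reply is that the text can be reconciled as it stands. Section 9.4.5 can be read as a general rule that already puts both baselines into every efficacy model, and 9.4.1.2 does not call its list complete. Alternatively, 9.4.5 can be read as the union of the lists in 9.4.1.1 (baseline pain) and 9.4.1.2 (the endpoint's own baseline), in which case nothing conflicts. Section 9 also leaves detail to an SAP still to be written. This stands to the extent that the point is a clarification and not a demonstrated wrong analysis. But the two reconciliations lead to different models for the same three endpoints, so one sentence still has to settle it.

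The second reply is that the size rests on assumed inputs. That stands in full. With r near zero, which is plausible for goniometer-measured external rotation, the gain is negligible, and the rate of opposite verdicts shrinks with it.

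A reader might also infer that the fixed analysis-site effect in 9.4.1.1 and 9.4.1.2 is an error that undermines the stated power and should become a random intercept. The documents do not support that. Fixed site terms are valid. Analysis site is undefined, but physical sites are called study sites (9.1.1: "Demographic and Baseline characteristics will be listed by study site and patient"), so it may well mean pooled sites. With 10 levels and an assumed 20% of variance explained by covariates, a single-outcome calculation on the Week 12 inputs keeps power at 87.8% (OA) and 90.0% (AC). Large losses need about 35 unpooled levels in each cohort, and they are smaller in a repeated-measures model than in a single-outcome one. Pairing them with the upper end of the SD range in 9.4.3 at the initial sample sizes also overlooks the increase to 150 per condition allowed there. A random site intercept is an optional choice.

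**Conclusion.** The point holds as an inconsistency in the specification of three sequentially tested endpoints, with a small and nearly free efficiency gain from resolving it towards 9.4.5. At a standardised effect of 0.5 the gain is about 0.4 points of power at r = 0.1, 1 to 2 at r = 0.2, and 5 to 6 at r = 0.4. The effect size, r and the block size are assumptions. The calculation treats Week 12 as a single complete outcome, not as part of the repeated-measures model.

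A reader might infer that leaving out a stratification factor biases the estimate or invalidates the test. It does neither: the error rate falls slightly below 5%. The primary analysis is also untouched, because 9.4.1.1 uses "an Analysis of Covariance model with parameters for treatment group, Baseline average daily shoulder pain with movement score, and analysis site", which already contains baseline pain. So is Week 12 pain, the first secondary endpoint.

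**What to change.** Amend 9.4.1.2 so that the models for SPADI pain, SPADI disability and external rotation include baseline average daily shoulder pain with movement as well as the endpoint's own Baseline score, matching 9.4.5 and the synopsis. Pain duration for AC is already there. Carry the same wording into the SAP before unblinding.

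The cost is one degree of freedom per model. No new data are needed: eligibility already requires a baseline pain mean from at least 5 of the 7 days before Day 1. No change to the site terms is required.

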## **9 STATISTICS**

A comprehensive Statistical Analysis Plan (SAP) will be written and approved prior to database lock for this study. Each shoulder condition will be analyzed completely separately. In general, the same analysis methods will be used for both shoulder conditions, and any differences in analyses between the shoulder conditions will be detailed in the SAP.

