#### 9.4.1.3 Exploratory efficacy analyses

Area under the curve and continuous exploratory efficacy endpoints will be analyzed similarly to the primary and key secondary endpoints for each shoulder condition. Categorical endpoints will be compared via chi-square or exact tests depending on incidence rates. No adjustments will be made for multiplicity for exploratory efficacy endpoints.

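### The key secondary mixed model lets treatment vary by week but holds the Baseline slope constant; adding Baseline-by-week is a cheap safeguard for modest precision and dropout risks

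*Combined protocol and SAP*

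**What the plan says.** Section 9.4.1.2 analyses the key secondary change-from-Baseline endpoints with a longitudinal mixed model that has "fixed effects for treatment group, study week, treatment-by-week interaction, analysis site, and Baseline score". It adds "Patient will be the random effect" and, for adhesive capsulitis (AC), a covariate for pain duration. No within-patient covariance structure is named. On missing data it states "This model assumes data are missing at random and includes only observed data".

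The model covers four of the five secondary endpoints in 7.1.2: Week 12 pain with movement, SPADI pain, SPADI disability ("Change from Baseline in the SPADI disability subscale at Week 12") and external rotation. PGIC is a score without a Baseline. Section 9.4.1.3 extends the approach: "continuous exploratory efficacy endpoints will be analyzed similarly to the primary and key secondary endpoints".

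Section 9.4.5 again lists Baseline only as a main effect ("Baseline score for the endpoint, analysis site, and, for AC patients, pain duration since onset") and adds "Other covariates may be explored and will be fully defined in the SAP". Section 9 says "A comprehensive Statistical Analysis Plan (SAP) will be written and approved prior to database lock for this study"; no SAP model text is in the document supplied. No section mentions a Baseline-by-week term.

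**The concern.** When the outcome is change from Baseline, its slope on Baseline at week t is the regression coefficient of the week-t score on Baseline, minus 1. Unless Baseline predicts Week 1 and Week 24 equally well, that slope differs by week. One coefficient for all weeks is then a compromise.

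Two things could follow. First, chance Baseline imbalance between arms is removed incompletely at a given week, so the estimate is noisier. Second, missing at random protects the Week 12 estimate only if the mean model is adequate. For a patient who has left, the model predicts Week 12 from the common slope and from that patient's earlier residuals, and both carry the Baseline misfit. These endpoints are tested in sequence under type I error control, so it is reasonable to want the mean model right.

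**Working it through.** **The plan's own figure.** Section 9.4.6 sizes each cohort on Week 12 pain with movement, two-sided alpha 0.05, 1:1. With power = Φ(difference / (SD × √(4/N)) − 1.96):

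- Osteoarthritis (OA): 1 / (2 × √(4/136)) = 2.92, power 83.0%.
- AC: 1.2 / (2.1 × √(4/114)) = 3.05, power 86.2%.

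Both agree with the stated power above 80%. Neither uses a Baseline slope, so no stated figure depends on this point.

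**Precision with complete data.** Let β_t be the true slope at week t and β_c the common slope. The variance of the week-t treatment difference rises by (β_t − β_c)² × Var(Baseline) / residual variance at week t.

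Assumptions, none from the documents: equal SDs at all visits (set to 1), so β_t = ρ_t − 1 and residual variance = 1 − ρ_t²; visits at Weeks 1, 4, 8, 12, 16, 20 and 24; correlation between any two visits = s + d × exp(−gap in weeks/τ). Two settings:

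- Stronger decay (s 0.35, d 0.55, τ 8): ρ about 0.84, 0.47 and 0.38 at Weeks 1, 12 and 24.
- Milder decay (s 0.50, d 0.40, τ 12): ρ about 0.87, 0.65 and 0.55.

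Under an unstructured covariance, β_c is the generalised-least-squares weighted mean of the β_t, which leans toward the early visits. Under a patient random effect alone it is their simple mean.

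| Case | Stronger decay | Milder decay |
|---|---|---|
| Week 12, unstructured | (−0.527 + 0.307)² / 0.776 = 6.2% | (−0.353 + 0.213)² / 0.581 = 3.4% |
| Week 12, random effect | (−0.527 + 0.466)² / 0.776 = 0.5% | (−0.353 + 0.323)² / 0.581 = 0.2% |
| Week 12, unstructured, no Week 1 | (−0.527 + 0.453)² / 0.776 = 0.7% | (−0.353 + 0.296)² / 0.581 = 0.6% |
| Week 1, random effect | (−0.165 + 0.466)² / 0.303 = 30% | (−0.132 + 0.323)² / 0.247 = 15% |

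Over a wider set of correlations, the first row runs from about 1 to 9%, the second and third stay under 1%, and the last runs from about 6 to 45%. The third row matters for external rotation: 7.1.2 and 7.1.3 list range-of-motion endpoints from Week 4 onward, although 6.5.1 collects the measurement at Week 1.

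For a hypothetical endpoint with exactly 80% power (1.96 + 0.84 = 2.80), 6.2% more variance gives Φ(2.80/√1.062 − 1.96) = about 78%, and 3.4% gives about 79%. Simulation of 6,000 trials at 57 per arm with unstructured covariance gave power with versus without the interaction of 78.0 v 76.7%, 79.5 v 78.7% and 79.6 v 78.3%.

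A separate simulation (N = 136; Baseline SD 18, residual SD 20; slopes drifting linearly from −0.3 to −0.7 or from −0.1 to −0.9) found almost no Week 12 loss. Empirical standard errors were 3.54 v 3.54 and 3.05 v 3.05. Week 12 is the fourth of seven visits, so its slope is the average (−0.5) in both settings and misfit there is near zero by construction. Under the random effect, the reported standard error rose by up to about 3% (3.54 v 3.45).

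**Bias.** For leavers, the prediction error is roughly k × (their Baseline minus the mean), with k common to both arms. The error in the treatment difference is therefore k × (p_F × d_F − p_P × d_P), where p is the proportion missing, d is the leavers' mean Baseline departure, and F and P are FX006 and placebo. It is zero without dropout, without slope drift, or when p × d is equal in the two arms. Results for one slope minus interaction, true SPADI difference −10, about 18% missing at Week 12:

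- No dropout: 0.00. Same Baseline dependence in both arms: at most 0.01.
- Dependence in placebo only: −0.32 to −0.79, or 3 to 8% of the effect.
- Opposite dependence in the two arms (an extreme case): −0.67 to −1.66, or 7 to 17%.

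Under the decaying correlations at 57 per arm, with dropout after Week 4 of 20 to 30% on placebo and 10% on FX006, the overstatement was 0.015 to 0.05 residual SD. An effect with 80% power is 2.80 × √(2/57) = 0.52 SD, so this is 3 to 10% of it. The simulated models omitted site.

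**The case against.** The strongest reply is that the harm is small and rests on inputs that the plan does not supply. There are no SPADI or range-of-motion SDs, correlations, slopes by week or dropout rates. The only stated structure is a patient random effect, under which the Week 12 sampling loss is under 1%. The SAP is still to be written and may add covariates. All of this stands, and it limits the point to what may happen.

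A reader might infer that any dropout related to Baseline biases the Week 12 difference. It does not: when the relation is the same in both arms, the error cancels. A reader might also infer that the SPADI and external rotation results are certain to be mis-adjusted, or that the planned power is wrong. The documents support neither. The slopes are unknown, and the power statement concerns pain with movement, where the entry range of 5.0 to 9.0 and stratification at 7.0 restrict Baseline spread and imbalance.

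The reply does not remove the restriction itself. Section 9.4.1.2 already names the model, and the opening in 9.4.5 is for other covariates, not for a changed form of one already listed. Lack of efficacy is a listed withdrawal reason and withdrawn patients are not replaced (4.3), so dropout that differs by arm and severity cannot be ruled out in a placebo-controlled pain trial.

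**Conclusion.** The point holds as a modest, conditional weakness. As written, one Baseline slope serves all weeks while the treatment effect is free by week.

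- **Precision at Week 12:** roughly 1 to 9% of variance with an unstructured covariance including Week 1; under 1% with the patient random effect alone or without Week 1. At an assumed 80% power, that is about one or two points in the cases worked through.
- **Precision at Week 1 (exploratory):** about 6 to 45% of variance under the patient random effect.
- **Bias at Week 12:** essentially none with complete data or with Baseline-dependent dropout that is alike in both arms. About 3 to 10% of the effect in plausible cases where slopes drift and the Baseline-dropout relation differs by arm. It favours FX006 if high-Baseline placebo patients leave more, and the reverse pattern reverses it.

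Every size rests on assumed correlations, SDs and dropout. That the slope drifts at all is likely but not documented. This is an improvement of low-to-moderate priority, not an error in a stated figure.

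**What to change.** In 9.4.1.2 and in the SAP, replace the single Baseline term with *Baseline score and Baseline score-by-week interaction*. Apply it to every key secondary change-from-Baseline endpoint analysed with this model, including Week 12 pain with movement, and to the exploratory models that follow it under 9.4.1.3. Name the within-patient covariance structure in the same edit, since the size of the loss depends on it.

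The cost is one degree of freedom for each week in the model after the first: 6 for seven visits, or 5 for range of motion if Week 1 is not modelled. It needs no new data or patients and changes neither the sample size nor any stated power. It should be settled before database lock, when the SAP is due for approval.

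### The key secondary repeated-measures model states no within-patient covariance beyond a patient random effect; fitted as a random intercept alone, it may misstate the Week 12 standard errors

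*Combined protocol and SAP*

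**What the plan says.** Section 9.4.1.2 of the protocol sets out how changes from Baseline in the key secondary family are handled. They "will be analyzed with longitudinal mixed models for repeated measures with fixed effects for treatment group, study week, treatment-by-week interaction, analysis site, and Baseline score". Pain duration since onset is added for adhesive capsulitis. On dependence within a patient there is one sentence: "Patient will be the random effect". On missing data, "This model assumes data are missing at random and includes only observed data". The section then claims "overall type I error control at the 2-sided 0.05 level" for the sequential family.

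Section 7.1.2 places all five key secondary endpoints at Week 12. Four are changes from Baseline and fall under this model: pain with movement, SPADI pain, SPADI disability and external rotation. The fifth, the PGIC, is not a change from Baseline. Section 9.4.1.3 carries the approach further: "continuous exploratory efficacy endpoints will be analyzed similarly to the primary and key secondary endpoints for each shoulder condition". Section 7.1.3 lists those endpoints at visits out to Week 24.

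The reviewed text names no residual covariance structure, fallback structure, robust variance or degrees-of-freedom method. It also does not say that residuals are independent or have equal variance. Section 9 promises more detail: "A comprehensive Statistical Analysis Plan (SAP) will be written and approved prior to database lock for this study". No separate SAP text is in the reviewed document.

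**The concern.** A random patient intercept with independent, equal-variance residuals is compound symmetry: one variance for every week and one correlation for every pair of weeks. A programmer who takes Section 9.4.1.2 at its word and accepts software defaults will fit exactly that.

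Under that fit, the standard error for the treatment difference at any week uses a variance pooled over all weeks. Change scores often vary less soon after Baseline than later. If the spread at Week 12 is above the average over follow-up, the Week 12 standard error is too small and the test rejects too often. If it is below the average, the test is conservative.

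At stake is the plan's own claim of 0.05 control for the Week 12 family. The first member of that family is "Change from Baseline in the weekly mean of the average daily shoulder pain with movement score at Week 12", the endpoint on which Section 9.4.6 bases the sample size. The exploratory estimates at early and late weeks are also exposed, possibly more so, because those weeks lie furthest from the average.

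**Working it through.** **1. The plan's own figure.** Section 9.4.6 gives 136 OA patients (68 per arm; difference 1, SD 2) and 114 AC patients (57 per arm; difference 1.2, SD 2.1), with power above 80%.
- Formula: power = Φ(difference / (SD × √(2/n)) − 1.96).
- OA: SE = 2 × √(2/68) = 0.343, power 83.0%.
- AC: SE = 2.1 × √(2/57) = 0.393, power 86.2%.

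The power statement reproduces. The plan gives no figure for the point at issue, so everything below rests on assumed SD profiles.

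**2. Formula.** For complete, balanced data, compound symmetry estimates the total variance as the mean of the weekly variances. Hence:
- fitted SE / correct SE at week t = √(mean of weekly variances / variance at week t)
- two-sided type I error = 2 × (1 − Φ(1.96 × ratio))

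**3. Inputs.**
- Visits: Weeks 1, 4, 8, 12, 16, 20 and 24, the schedule for SPADI and range of motion in Table 1 (Appendix A).
- SD at Week 12: 2.0, the OA planning value. Only the relative profile affects the ratio.
- SD at Week 1: 1.2 or 1.6, an assumption, with straight lines between stated points. The range 2 to 2.5 in Section 9.4.3 is uncertainty about the primary endpoint's SD, not a change over weeks, so it cannot serve here.
- No dropout and no covariates.

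**4. Results at Week 12.**

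| Assumed SD profile | Mean variance (start 1.2 / 1.6) | SE ratio | Type I error |
|---|---|---|---|
| Constant at 2.0 | 4.00 | 1.00 | 5.0% |
| Steady rise through Week 24 | 4.36 / 4.10 | 1.04 / 1.01 | 4.1% / 4.7% |
| Rise, flat from Week 8 | 3.40 / 3.67 | 0.92 / 0.96 | 7.1% / 6.0% |
| Rise, flat from Week 12 | 3.20 / 3.56 | 0.89 / 0.94 | 8.0% / 6.5% |
| Peak at Week 12, falling to 1.6 at Week 24 | 2.77 / 3.14 | 0.83 / 0.89 | 10.3% / 8.2% |

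Worked line (flat from Week 12, start 1.2): SDs 1.2, 1.418, 1.709, 2, 2, 2, 2; mean variance 3.196; ratio √(3.196/4) = 0.894; error 2 × (1 − Φ(1.752)) = 8.0%. In OA the SE would be 0.307 instead of 0.343.

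**5. Other weeks.** Under the steady rise, the Week 24 SD is 2.87 (start 1.2) or 2.44 (start 1.6). The ratios are 0.73 and 0.83, with error 15% and 10%. At Week 1 the ratios are 1.74 and 1.27, with error 0.1% and 1.3%.

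**6. Check with dropout.** A simulation used seven visits, 68 per arm, no treatment effect, about 15% dropout missing at random and 1,000 runs per profile. It compared a random-intercept fit with an unstructured fit at Week 12.

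| SD profile | Random intercept | Unstructured |
|---|---|---|
| Constant 2.0 | 5.4% | 5.7% |
| Linear 1.5 to 2.3 over 24 weeks | 4.7% | 4.3% |
| 1.0 to 2.5 by Week 12, then flat | 10.5% | 5.3% |

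Across Weeks 1, 12 and 24 the unstructured fit stayed between 4.3% and 5.7%. The third profile is steeper than any in step 4.

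**The case against.** The strongest reply is that the protocol is silent on the residuals and does not specify the wrong ones. It calls the analysis a mixed model for repeated measures, and a patient effect does not exclude a week-specific residual covariance. Covariance structure and degrees of freedom are ordinary SAP content, and an SAP is promised. This stands. A reader might infer that the plan forces equal variances and gives wrong standard errors at Week 12. The documents do not support that, because equal-variance residuals are one reading of the text, not something it states.

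A second reply is that harm depends on the profile. With a constant or steadily rising SD there is no inflation at Week 12, which sits near the middle of follow-up. Inflation needs a plateau or peak by about Week 12, and starting at 1.2 implies nearly a threefold rise in variance (4.00/1.44 = 2.8). This also stands, which is why the milder start of 1.6 and the no-inflation cases are shown.

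A third is reach. The primary test is an ANCOVA on AUC (Section 9.4.1.1), and the worst figures fall at weeks that are exploratory and carry no multiplicity adjustment. That is correct.

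The appeal to the SAP does not close the matter. Section 9.4.1.1 defers its AUC details to the SAP explicitly, whereas Section 9.4.1.2 states a model and makes no such deferral. Section 9 requires the SAP only before database lock.

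**Conclusion.** The point holds as a gap in specification with a possible consequence. The patient random effect is the only stated source of within-patient correlation. The literal default fit can misstate the Week 12 standard errors for four of the five key secondary endpoints.

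Under the assumed seven-visit profiles the Week 12 type I error runs from 4.1% to about 10%, with 5.0% when the SD is constant. The documents contain no week-specific SDs, so neither the existence nor the direction of an error can be established from them. The Week 1 and Week 24 figures concern exploratory estimates only. The primary analysis and the PGIC are unaffected. Any effect of a misspecified covariance on the missing-at-random argument was not separately quantified and is not part of this conclusion.

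It should be fixed, because the remedy is standard, costs little and protects a type I error claim that the plan itself makes.

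**What to change.** Replace the random-effect sentence in Section 9.4.1.2, and carry the same text into the SAP, along these lines: within-patient errors follow an unstructured covariance matrix across Weeks 1, 4, 8, 12, 16, 20 and 24; degrees of freedom are Kenward-Roger; no patient random effect is included; if the model does not converge, heterogeneous Toeplitz and then heterogeneous AR(1) are used, in that order.

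Naming the weeks matters for the diary pain score. Seven weeks need 7 × 8 / 2 = 28 covariance parameters, which 114 to 136 patients can support. All 24 weekly means would need 24 × 25 / 2 = 300.

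A Baseline-by-week interaction may be added but is optional; its effect was not quantified.

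The cost is wording and a standard software option. The small downside is more covariance parameters and some risk of non-convergence, which the fallback order handles. Neither the sample size nor data collection changes.
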